The primary outcome model will be a hierarchical mixed model (i.e., GLMM) that will include time (categorical; baseline, mid-point, and end-of-treatment), treatment (app-CBT vs. supportive attentional control), and their interaction as fixed effects, and will model time as a repeated measure using either an autoregressive (AR1), Toeplitz, compound symmetry, or unstructured covariance matrix, based on best fit determined by AIC and BIC. The unstructured covariance matrix model will only be used if this model fits significantly better than alternative simpler models, based on -2 log likelihoods. The main hypothesis test will be based on a specific contrast of treatment difference at week 12. Because these analyses will include all subjects who are randomized and complete at least one assessment, it is an intent-to-treat analysis. These analyses will include only the 3 assessments from baseline to post-treatment and will not include the 3-month or 12-month follow-up (FU) assessments, because treatment response could be affected by subjects seeking other treatments during the FU period. Between-group effect sizes will be calculated using Cohen's *d*. This analysis will then be repeated using the per-protocol sample.

In addition to the analyses specified above, we will describe the proportion of subjects in each treatment arm who achieve response, where response is defined as a 25% or greater reduction in Y-BOCS score from baseline to end of treatment (week 12) (Storch et al., 2006). While no formal comparisons will be made between treatments, the reporting of response rates is clinically useful and will facilitate comparison to other studies in the field. We will report response as observed (excluding subjects with missing data at week 12) and will additionally examine how rates may change when a) applying a last observation carried forward approach, and b) conservatively considering subjects with missing week 12 scores as non-responders.

Secondary endpoint: Difference in secondary clinical outcomes (i.e., QIDS-SR, WSAS, Q-LES-Q-SF) at the end of treatment (i.e., preliminary efficacy for secondary symptoms)

Analysis:

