The sample size required to test a significant treatment response difference between the app-CBT and the control condition at the end of treatment is n=116 (n=58 per group). The sample size estimate is based on a single degree of freedom contrast in an ANOVA design, implemented in SAS for Windows version 9.4. The power model used a two-sided alpha=0.05, a power of 0.90, equal allocation of participants into both treatment arms, an assumption of an effect size of 0.76 comparing the two treatments at the end of treatment, as well as an assumption of a standard deviation of 1.1. The anticipated effect size of the app-CBT was conservatively based on the 95% lower confidence limit of the mean between-group effect size of CBT vs. psychological placebos reported in Ost et al. (g=1.29, 95% CI: [0.76–1.81]; Öst, Havnen, Hansen, & Kvale, 2015). We chose this conservative limit, because the effect sizes of recent, large RCTs of CBT or iCBT vs. various psychological control conditions have been quite variable, ranging from a high of d=1.12 in a comparison of iCBT against online non-directive supportive therapy (n=101; E.

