Andersson et al., 2012) to $d=0.55$ in a trial of iCBT vs. internet-based progressive relaxation therapy (n=179; Kyrios et al., 2018) and $d=0.52$ in a trial of CBT vs. stress management training (n=73; Whittal, Woody, McLean, Rachman, & Robichaud, 2010). In the process of evaluating effect sizes from previous trials, we did not differentiate between internet-delivered CBT and face-to-face CBT, because a meta-analysis including 13 RCTs that directly compared these two treatment modalities in patients with various psychiatric and somatic conditions (total N=1053) showed a pooled effect size (Hedges' g) at post-treatment of -0.01 (95% CI: -0.13 to 0.12; G. Andersson, Cuijpers, Carlbring, Riper, & Hedman, 2014); of note, though, this direct comparison has not been done in trials with patients with OCD. Furthermore, in the wake of the COVID-19 pandemic, various negative mental health states and stressors – including anxiety, worry, depression, loneliness, financial strain, and trauma symptoms – have increased in the US population (e.g., Fowers & Wan, 2020). The variability of these negative mental health states and stressors will likely be higher than during non-pandemic times as multiple waves of the pandemic and state-wide measures of social interaction restrictions sweep the nation in the foreseeable future. In response, we used a standard deviation of 1.1 (instead of the standardized 1.0) in our power calculations to allow for a 10% increase in the variability of symptom severity estimates during the ongoing effects of the COVID-19 pandemic and its socioeconomic aftermath. Lastly, we assumed a conservative drop-out rate of 20% by end of treatment, based on the dropout numbers reported in a meta-analysis of 18 studies targeting self-help treatments for OCD, where studies with self-administered treatment without therapist contact had a drop-out rate of approximately 40%, compared to drop-out rates of 17-20% in treatments with minimal to low therapist contact (Pearcy, Anderson, Egan, & Rees, 2016); the meta-analysis by Ost et al. (2015) reported an estimated dropout rate of 15.5% from in-person CBT treatment.

VII. RISKS AND DISCOMFORTS

A. Complications of surgical and non-surgical procedures

Not applicable

B. Drug side effects and toxicities

Not applicable

C. Device complications/malfunctions

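### No planned week-12 response rate is valid in general under the missing-at-random assumption that the primary model implies, and LOCF tends to understate app-arm response

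*Combined protocol and SAP*

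**What the plan says.** Section VI.C (Primary endpoint, Analysis) defines response as a Y-BOCS fall of at least 25% from baseline to week 12. The lead display is given as "We will report response as observed (excluding subjects with missing data at week 12". The plan then looks at how the rates move under two alternatives: "applying a last observation carried forward approach", and counting every missing week-12 score as non-response. No formal comparison of arms is planned for these rates. They are justified by clinical usefulness and by comparability with other trials.

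The primary analysis in the same section is a mixed model on baseline, week-6 and week-12 Y-BOCS. It includes every randomized participant with at least one assessment. The words missing at random do not appear; a likelihood-based model of this kind implies that assumption. The introduction to section VI also plans to examine whether drop-out is nonrandom and to compare dropouts with completers. Section VI.D states that "we assumed a conservative drop-out rate of 20% by end of treatment". No model-based or imputed response rate is planned.

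**The concern.** The headline result and the response rates come from the same Y-BOCS scores but treat missing ones differently. The mixed model lets observed baseline and week-6 scores inform what week 12 would have been. The three response displays do not. One drops people without a week-12 score, one freezes them at an earlier visit, and one fixes them as failures.

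The primary model has three visits, so LOCF has only two sources. A participant last seen at baseline has zero change and cannot be a responder. A participant last seen at week 6 is judged on a half-treatment score. If patients keep improving, both push the rate down, and more so in the arm that improves more.

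At stake is a number per arm that readers quote easily. They would see three rates, possibly several points apart, and none would estimate response under the assumption on which the main result rests.

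**Working it through.** **Inputs from the documents.** Drop-out of 20% by end of treatment (VI.D); visits at baseline, week 6 and week 12; the 25% rule (VI.C). The documents give no Y-BOCS means, no response rates by arm and no drop-out timing, so those are assumptions below.

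**Step 1: the plan's own figure.** Section VI.D uses "an assumption of an effect size of 0.76 comparing the two treatments at the end of treatment", an "assumption of a standard deviation of 1.1", two-sided alpha 0.05 and "a power of 0.90".
- Normal approximation: 2 × (1.960 + 1.282)² × (1.1/0.76)² = 44.02, so 45 per arm. 45/0.80 = 56.25, so 57 per arm, 114 in total.
- t-based: 45.006, so 46 per arm. 46/0.80 = 57.5, so 58 per arm, 116 in total.

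The stated 116 reproduces, with the 20% treated as lost week-12 data.

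**Step 2: formulas.** Let d be the share missing at week 12, p the week-12 response the missing would have shown, q the response among those observed, s the share of the missing who have a week-6 score, and r6 the week-6 response in that group. The true rate is (1 − d)q + dp. Then:
- observed-case error = d(q − p), which is zero when drop-out is unrelated to outcome;
- missing-as-non-responder deficit = dp;
- LOCF deficit = d(p − s·r6);
- gap between the last two displays = d·s·r6.

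**Step 3: numbers at d = 20%, with p = 55% assumed** (percentage points).

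| s | r6 | LOCF deficit | Missing-as-non-responder deficit | Gap |
|---|---|---|---|---|
| 0 | n/a | 0.20 × 0.55 = 11.0 | 11.0 | 0 |
| 0.5 | 15% | 0.20 × (0.55 − 0.075) = 9.5 | 11.0 | 1.5 |
| 0.5 | 45% | 0.20 × (0.55 − 0.225) = 6.5 | 11.0 | 4.5 |
| 1 | 15% | 0.20 × (0.55 − 0.15) = 8.0 | 11.0 | 3.0 |
| 1 | 45% | 0.20 × (0.55 − 0.45) = 2.0 | 11.0 | 9.0 |

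**Step 4: simulation, first set of assumptions.** Baseline mean 26; SDs 4.5, 5.5 and 6.5 at weeks 0, 6 and 12; correlations 0.65 (weeks 0–6), 0.50 (0–12) and 0.70 (6–12). The app-arm mean falls by 6 to 10 points, with 40% to 70% of the fall by week 6. Drop-out is 20%, either unrelated to scores or rising with the week-6 score (log-odds 0.8 per SD). True app-arm response runs from 46% to 73%.
- LOCF deficit: 3.4 to 14.7 points over all drop-out timings.
- Gap between LOCF and missing-as-non-responder: 0 if all drop-out is before week 6, 0.6 to 5.5 if half is, and 1.4 to 11.1 if all is after.
- Observed-case error: about 0 when drop-out is unrelated to scores; +1.2 to +2.4 when drop-out after week 6 depends on the week-6 score.

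**Step 5: simulation, second set.** Means at the three visits 26/22/18.5 (app) and 26/24.5/23 (control); SDs 5/6/7; correlations 0.60/0.45/0.75. Half of drop-out is before week 6, and drop-out depends on the last observed score.

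| App arm, % | True | Observed | LOCF | Missing as non-responder | Imputation |
|---|---|---|---|---|---|
| 20% missing, log-odds 0.1 per point | 56.3 | 57.4 | 47.7 | 46.0 | 56.3 |
| 25% missing, log-odds 0.2 per point | 56.2 | 58.5 | 45.4 | 44.3 | 56.3 |

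The LOCF deficits are 56.3 − 47.7 = 8.6 and 56.2 − 45.4 = 10.8 points. If instead all drop-out falls after week 6 and is unrelated to scores, LOCF gives 51.1% against 45.0% for missing-as-non-responder at 20% missing (gap 6.1), and 49.8% against 42.3% at 25% (gap 7.5). Over 10 to 25% missing and all timings, LOCF was low in every run on these inputs, by about 2.5 to 15 points.

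**The case against.** The strongest reply is that LOCF is not the lead rate. The plan reports observed cases first and uses the other two to show how far the rate can move, so a spread between them is intended. The observed-case rate is unbiased if drop-out is completely random, and otherwise was usually within about 3 points of the truth. With 58 × 0.8, or about 46, completers per arm, the standard error of a 56% rate is √(0.56 × 0.44/46), about 7 points. This stands, and it keeps the point small.

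Three further replies also stand:
- 20% drop-out need not mean 20% missing scores. Participants who withdraw are to be asked, with payment, to complete all assessments, and the H3.1 definition of drop-out also counts people who did not use the app or website. At 10% missing the LOCF deficit is about 3 to 6 points.
- Imputation recovers the truth in these simulations because the data were generated as multivariate normal and missing at random. They do not show how it performs with 58 per arm or with drop-out that depends on unseen scores.
- LOCF has some value for comparison with older trials that used it.

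A reader might also infer that the plan expects unequal drop-out, which would distort the arm difference under LOCF. The documents do not support that. H3.1 hypothesises that app-arm drop-out will not be higher, and tests one-tailed for the contrary.

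None of this supplies a response rate consistent with the primary model. Calling the rates descriptive does not settle the matter either, since the plan reports them for clinical use and comparison with other trials.

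**Conclusion.** The point holds as an optional improvement. No planned response rate is valid in general under the missing-at-random assumption that the primary model implies. LOCF is the weakest of the three displays, because it codes anyone last seen at baseline as a non-responder and tends to understate app-arm response when patients improve. The size is roughly 3 to 15 points. It rests on assumed response rates, 10 to 25% missing and varied drop-out timing; the 20% drop-out is the only one of these figures that the documents give.

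Two stronger readings are not supported. The first is a narrower bias stated as fact, such as 6 to 11 points: it needs response rates and timing that the documents do not state. The second is that LOCF merely duplicates missing-as-non-responder. They are equal only if all drop-out comes before week 6. If all comes after, they differ by about 2 to 8 points on the second set of inputs and by up to 11 on the first.

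Response is not among the endpoints in section VI.B. The primary contrast, its test and the sample size are unaffected.

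**What to change.** In section VI.C (Primary endpoint, Analysis), add one response rate per arm, in place of LOCF or beside it. Impute missing Y-BOCS scores separately by arm from baseline, week-6 and week-12 scores (for example 50 imputations). Apply the 25% rule after imputation, combine by Rubin's rules, and give a 95% interval for each arm. Keep the observed-case and missing-as-non-responder displays. Add no between-arm difference, interval or test, because the section rules out formal comparison of these rates.

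The cost is one sentence in the plan, a short program and a little more explanation in the report. If LOCF is dropped, there is no LOCF figure to set against older trials; keeping it beside the imputed rate avoids that. No extra data or participants are needed.
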